3.2 Clinical parameters

ECOG: Yes No

If yes, Date: / / (DD/MM/YYYY)

If yes, Score: 0 1 2 3 4

e-CRF instruction: a link shall be added allowing the physician to view the score variables

Karnofsky score: Yes No

If yes, Date: / / (DD/MM/YYYY)

If yes, score: 100% 90% - 80% 70% - 60% 50% - 40% 30% - 10% 0%

e-CRF instruction: a link shall be added allowing the physician to view the score variables

Arterial blood pressure

Examination: Yes No

If yes, examination date: / / (DD/MM/YYYY)

If yes, specify values: / mmHg (syst./ diast.)

3.3 Haematological and biochemical examination since last visit

Please fill in the following table:

Date of biological examination: ___ / ___ / 20___ (DD/MM/YYYY)

Haematological profile

Parameters	Value obtained	Value	Unit
Haemoglobin	 Yes  No  Not performed	 g/dL	 Other If other, specify: ___
Neutrophils	 Yes  No  Not performed	 /mm ³	 Other If other, specify: ___
Platelets	 Yes  No  Not performed	 10 ⁹ /L	 Other If other, specify: ___

Biochemical profile

Parameters	Value obtained	Value	Unit
Creatinine	 Yes  No  Not performed	 mg/dL	 Other If other, specify: ___
ALAT (GPT)	 Yes  No  Not performed	 U/L	 Other If other, specify: ___
ASAT (GOT)	 Yes  No  Not performed	 U/L	 Other If other, specify: ___
Total bilirubin	 Yes  No  Not performed	 mg/dL	 Other If other, specify: ___
Calcium	 Yes  No  Not performed	 mmol/L	 Other If other, specify: ___
Albumin	 Yes  No  Not performed	 g/L	 Other If other, specify: ___
LDH	 Yes  No  Not performed	 UI/L	 Other If other, specify: ___

Were abnormal values of other biological parameters observed (last available examination)? Yes No

Parameters	Value obtained	Abnormal result	For abnormal results, value	Unit
Haematology				
Haematocrit	 Yes  No  Not performed	 Yes  No		 %  Other If other, specify: ___
White blood cells	 Yes  No  Not performed	 Yes  No		 10 ⁹ /L  Other If other, specify: ___
Biochemistry				
Alkaline phosphatase	 Yes  No  Not performed	 Yes  No		 U/L  Other If other, specify: ___
TSH	 Yes  No  Not performed	 Yes  No		 mU/L  Other If other, specify: ___
fT3	 Yes  No  Not performed	 Yes  No		 pmol/L  Other If other, specify: ___

fT4	 Yes  No  Not performed	 Yes  No		 pmol/L  Other If other , specify: _____
Sodium	 Yes  No  Not performed	 Yes  No		 mmol/L  Other If other , specify: _____
Potassium	 Yes  No  Not performed	 Yes  No		 mmol/L  Other If other , specify: _____

3.4 Symptoms and tolerance since last visit

Since the last visit dated [date of last recorded visit], **has the patient presented with:**

Skin reactions or disease: Yes No *If yes*, how many episodes: _____

Digestive disorders: Yes No *If yes*, how many episodes: _____

Heart disorders: Yes No *If yes*, how many episodes: _____

Haemorrhagic disorders: Yes No *If yes*, how many episodes: _____

Haematological disorders: Yes No *If yes*, how many episodes: _____

Infections: Yes No *If yes*, how many episodes: _____

Pains: Yes No *If yes*, how many episodes: _____

If yes, specify the location: _____

Endocrine disorders: Yes No *If yes*, how many episodes: _____

Inflammatory disorders (mucositis, etc.): Yes No *If yes*, how many episodes: _____

General symptoms (asthenia, anorexia, etc.): Yes No *If yes*, how many episodes: _____

Occurrence of other adverse events Yes No *If yes*, how many episodes: _____

If yes, specify: _____

In the instructions for completing the AE report form, insist on:

'please give a precise description of the event, its duration, its impact on the patient's life, the corrective measures implemented and any medical procedures required: medical consultation, A&E department, hospitalisation'

'please evaluate the degree of severity of this case according to CTCAE v4.03 (June 2010)'

'please fill in the adverse event report form for all AEs, whether serious or not, whether associated with the sunitinib treatment or not'

e-CRF instruction: Pharmacovigilance form: Each time a table row is validated, the participating physician is directed to a form to be filled in.

Description of the adverse effect:

Type of event	Description of the event	Start date	Severity	Grade (CTCAE v4.03)	Impact on activities of daily living:	Causal relationship	Change	Corrective medical action	Last action performed on Sutent® during the adverse event
Overview of all previous AEs (e-CRF + CATI) and follow-ups									

(auto)	--/--	 Non-serious  Serious If serious, severity criteria (several possible answers):  Caused death If death, specify: Date of death: --/---/--- (DD/MM/YYYY) Cause of death: _____  Life-threatening  Hospitalization / prolonged hospitalization  Anomaly / congenital malformation  Permanent or major invalidity or disability  Medically significant event	 Grade 1  Grade 2  Grade 3  Grade 4  Grade 5	 Does not affect daily life  Makes certain actions difficult to accomplish  Affect activities of daily life	 Related to taking Sutent®  Related to a concomitant medicine If other, specify the treatment _____	 Recovered If recovered, recovery date: --/--/-- (DD/MM/YY YY)  Recovered with sequelae If recovered, recovery date: --/--/-- (DD/MM/YY YY)  Recovering  Not recovered  Unknown	 Prescription of a treatment, specify:  Medical consultation (general practitioner, specialist, emergency department) →§3.7  Hospitalisation. →§3.7  Other, specify:  Not applicable	 Interruption (temporary, permanent, or delayed) If causality = Sutent®, →§3.5  Dose reduction If causality = Sutent®, →§3.5  Dose increase If causality = Sutent®, →§3.5  Dose unchanged  Unknown  Not applicable
---------	-------	-------	--	--	---	--	---	--	---

(Dynamic table: auto-incrementation of the number of rows displayed according to the number of AEs declared above. The

table is shared with that of AEs declared by the nurses using the CATI system).

3.5 Conditions of use of the sunitinib treatment

Has the sunitinib dose and/or dosage regimen been changed since the last documented visit dated [date of last recorded visit], including during the day's follow-up visit?

Yes No

If yes, describe all modifications observed:

Date	Change of dose	If yes, new dose (mg/day)	Change of dosage regimen	If yes, new regimen	Reason for the modification
__/__/__ (DD/MM/YYYY)	 Yes  No	 25  37.5  50  62.5  75  Other: __	 Yes  No	: _____	 AE; If yes, specify which one: _____  Other, specify: _____
__/__/__ (DD/MM/YYYY)	 Yes  No	 25  37.5  50  62.5  75  Other: __	 Yes  No	: _____	 AE; If yes, specify which one: _____  Other, specify: _____

(Dynamic table: rows can be added if more than two modifications are observed)

*: If AE ticked, the physician has already described this AE in the previous section, the e-CRF will thus display the list of AEs already filled in and the physician can simply select the relevant AE (without having to describe it again)

Has the sunitinib treatment been temporarily interrupted since the last documented visit dated [date of last recorded visit], including during the day's follow-up visit? Yes No

If yes, describe each interruption:

Date	Duration	If yes, reason for interruption
____/____/ _____ (DD/MM/YYYY)	____ days  Ongoing	 AE*; If yes, specify which one: _____  Radiotherapy  Surgery  Other, specify: _____
____/____/ _____ (DD/MM/YYYY)	____ days  Ongoing	 AE; If yes, specify which one: _____  Radiotherapy  Surgery  Other, specify: _____

(Dynamic table: rows can be added if more than two modifications are observed)

*: If AE ticked, the physician has already described this AE in the previous section, the e-CRF will thus display the list of AEs already filled in and the physician can simply select the relevant AE (without having to describe it again)

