7.3.2 Secondary outcome measures

Each of these criteria shall be evaluated based on the data collected via the e-CRF by the physicians and via a self-questionnaire provided to the patients.

- Dose reduction, treatment interruptions and termination (sunitinib)

Description of dose reduction

- Proportion of patients having had at least one dose reduction relative to the initial dose
- Reasons for dose reduction
- Change of dose (initial dose and new dose prescribed)

Description of treatment interruptions

- Proportion of patients having temporarily interrupted their sunitinib treatment (including postponement of the start of the subsequent cycle)
- Mean interruption duration
- Cause for the interruptions

Treatment termination

- Proportion of patients having stopped taking sunitinib
- Reasons for termination

- Unforeseen medical procedures:

- Mean number of unforeseen consultations
- Mean number of unscheduled hospitalisations

Unforeseen medical procedures correspond to unscheduled consultations and hospitalisations, whether associated with sunitinib or not.

- Treatment compliance

Treatment compliance shall be evaluated directly with the patients using the standardised questionnaire validated by Morisky, available in appendix 9 of the protocol. This generic therapeutic compliance evaluation questionnaire comprises 4 questions scored as 0 for "YES" and 1 for "NO". The points for each question are added up to obtain a score ranging from 0, if all questions are answered by "yes" (reflects poor compliance) and 4, if all questions are answered by "no" (reflects good compliance).

It shall be completed, during the routine follow-up visit with the participating physician, after the sixth week of cycles 1, 2 and 4, via a self-questionnaire issued to the patient.

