3.8 Decision concerning sunitinib treatment

Participating physician's decision following this follow-up visit

Continue treatment, date of day 1 of next cycle: ____ / ____ / ____ (DD/MM/YYYY)

Dose and dosage regimen:

50 mg/day, 4 weeks followed by a 2-week break

Other, specify: _____

Termination of current treatment, date stopped: ____ / ____ / ____ (DD/MM/YYYY)

Break from therapy

Change of line of therapy (fill in the end of treatment appraisal form)

Continued break from therapy

Resumed sunitinib treatment, date resumed: ____ / ____ / ____ (DD/MM/YYYY)

In the event of treatment termination, the physician is directed to the end of treatment form.

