7. MANAGEMENT OF MISSING VALUES

The data from patients were recorded on an eCRF, except for the paper self-completed adherence and patient satisfaction questionnaires. Mandatory fields and consistency controls will be used to check data registered at the time. This strategy will be used to reduce missing data points or inconsistencies, particularly those concerning the major end points (AE, grades of AE and response to treatment etc.).

The analyses will be performed on the available data (“observed case analysis”), using the assumption that missing data are non-informative. The numbers of missing data points will be presented for each variable.

The response analysis will also be conducted on the FAS population by imputing missing responses as failure (= progression).

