8.2.5. Analysis of the secondary end points

8.2.5.1. Sunitinib treatment

Populations analyzed: Safety population

End points:

The analysis of sunitinib treatment methods will be carried out using the following indicators:

▪ **Description of dose reductions**

- Proportion of patients with at least one dose reduction during the period of sunitinib treatment;
- Reasons for the dose reduction: Proportion of patients involved on at least one occasion for each of the reasons for a dose reduction;
- Average dose reduction.

▪ **Description of interruptions to treatment**

- Proportion of patients who interrupted sunitinib treatment temporarily during treatment (including declared temporary interruptions and cases in which the start of the later cycle was deferred);
- Mean duration (in days) of interruptions to treatment by patient (declared duration of interruption or number of days delay identified for the start of the subsequent cycle);
- Reason for interruptions: Proportion of patients involved on at least one occasion for each of the reasons for interruption of treatment (AE, radiotherapy, surgery or other).

▪ **Description of permanent treatment discontinuations**

- Proportion of patients who discontinued sunitinib permanently;
- Reason for discontinuation: proportion of patients involved on at least one occasion for each of the reasons for discontinuation;
- Duration of treatment with sunitinib: time between starting sunitinib and the notified date to discontinue it or the date of the last consultation if sunitinib treatment was not stopped;
- Number of treatment cycles before discontinuation.

The analysis will be performed both on an overall basis and according to the number of calls made by the call center.

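### The SAP has no rule for interruptions still open at a visit, so mean interruption duration will tend to come out too low

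*Protocol*

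**What the plan says.** Protocol 7.3.2 lists "Mean interruption duration" among the secondary measures, and SAP 6.2 repeats it.

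- **Collection.** CRF 3.5 (Protocol Appendix 6) covers the time since the last documented visit, "including during the day's follow-up visit". If treatment was interrupted, the physician is to "describe each interruption". Each row has a start date, a reason, and one duration cell with a blank for days and an 'Ongoing' box. There is no end date. Nothing tells the physician to return to an open row at the next visit, or says whether the days stay blank when 'Ongoing' is ticked.
- **Definition.** SAP 8.2.5.1 counts as interruptions "including declared temporary interruptions and cases in which the start of the later cycle was deferred". Duration, averaged by patient, is the "declared duration of interruption or number of days delay identified for the start of the subsequent cycle".
- **Missing values.** SAP 7 uses available data, "using the assumption that missing data are non-informative". Its only imputation rule is for tumour response.
- **Dates held elsewhere.** CRF 3.8 has entries for "Resumed sunitinib treatment, date resumed" and "Continue treatment, date of day 1 of next cycle". The nurse script (Protocol Appendix 7, D.2.2.1) asks for a resumption date at the first call of cycles 2, 3 and 4.
- **Output.** SAP Table 34 shows number analysed, mean, SD, median and range, with no line for open interruptions.

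**The concern.** For any given start date, a longer interruption is more likely to reach the next visit unfinished. If an unfinished row has no duration and is left out, the rows that remain are weighted towards short interruptions. Missingness then depends on the quantity being averaged, which is what the SAP 7 assumption excludes.

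The summary may concern many patients: Protocol 6.1.2 cites earlier data in which 61.6% of patients had at least one cycle postponed, and the SAP counts deferred cycles as interruptions. Understated durations would make treatment management under the call centre look better than it was.

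**Working it through.** The plan gives no figure for interruption duration, so there is none to reproduce. The inputs from the documents are visits at about W6, W12 and W24 (days 42, 84 and 168), 6-week cycles, and the starting regimen in CRF 2.8 of 4 weeks on and 2 weeks off. Everything about durations below is assumed.

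**Step 1: the mechanism.** Let half of interruptions last 7 days and half 28, so the true mean is 17.5. The chance that a duration is kept is the share of onset days from which it ends before the visit.

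- 42-day gap, onset on any day: kept 1 - 7/42 = 0.833 and 1 - 28/42 = 0.333. Mean of kept rows = (0.833×7 + 0.333×28)/1.167 = 13.0; 42% of rows lost.
- 42-day gap, onset on days 0 to 28 only: a 7-day hold always ends in time and a 28-day hold half the time. Mean = (1×7 + 0.5×28)/1.5 = 14.0; 25% lost.
- 84-day gap (W12 to W24), onset on treatment days only: kept 1 and 0.75. Mean = (7 + 21)/1.75 = 16.0; 12.5% lost.

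**Step 2: what the delay route recovers.** Suppose treatment stops on day 15 and the next cycle, due on day 43, starts on day 50. The delay is 50 - 43 = 7 days. Treatment days 15 to 28, 14 in all, were also missed. Read literally, the delay counts 7 of 21 missed treatment days.

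**Step 3: size under three handling rules.** I simulated 400,000 interruptions per scenario, with onset on treatment days only, on any day, or on any day with 20% starting at a visit. Durations run in calendar days. Bias of the mean at an assumed true mean of 14 days:

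| Handling of open rows | Exponential durations | Gamma (shape 2) durations |
|---|---|---|
| A. All dropped | -24% to -29% | -13% to -16% |
| B. Rows open at W6/W12 closed from dates; W24 rows dropped | -8% to -9% | -4% to -5% |
| C. Rows open at W6/W12 counted as days after the visit only; W24 rows dropped | -20% to -24% | -15% to -18% |

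Over true means of 7 to 28 days with variable durations, A runs from -2% to -48%, B from -1% to -16%, and C from -3% to -36%. With constant durations, A and B give 0% and C gives 0% to -21%. Across all scenarios, 0% to 20% of interruptions are open at W24.

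The simulation averages over interruptions. The SAP averages by patient, so a patient with another completed interruption stays in, and the bias there could differ.

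**The case against.** A reader might infer that open interruptions are never closed, that the longest ones drop out, and that the mean will be about a quarter too low (13.0 against 17.5 days is -26%). The documents do not support that reading, for four reasons.

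- **SAP 8.2.5.1 does not rely on declared durations alone.** Visits fall at the end of cycles, so many holds open at W6 or W12 will show up as a delayed next cycle. This stands, but Step 2 shows that the delay can miss days lost before the scheduled start.
- **Closing dates exist.** CRF 3.8 and the nurse calls collect them, and the protocol provides for queries on incomplete data (8.2 and 8.6.3). This also stands. Yet nothing tells the analyst to complete an 'Ongoing' row from these dates. There is no end-of-cycle-3 visit. Protocol 7.3.2 names the physician e-CRF and self-questionnaires as the sources for secondary measures, so nurse-call dates are supporting evidence only.
- **Long holds are more likely to be lost, not certain to be.** A hold decided on the visit day is ongoing whatever its final length.
- **The -26% needs two assumptions:** onset spread over rest days as well as treatment days, and every open row discarded. Restricting onset to treatment days gives 14.0 days (-20%), and the SAP does not say that open rows are discarded.

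It is also fair that no tests are planned (SAP 4.1) and that Table 34 gives the median and range. Those rest on the same rows, however. A patient leaves the study after four cycles (Protocol 8.2, End of study), so no later study visit can close or confirm a row open at W24.

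**Conclusion.** The point holds as a gap in the SAP with a predictable direction. Open interruptions have no handling rule, and the missing-data assumption in SAP 7 does not suit them. Mean interruption duration will tend to be too low whenever durations vary.

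The size cannot be fixed from the documents. At an assumed mean of 14 days with variable durations it lies between about -4% and -29%, depending on which of the three handling rules is used. The low end (-4% to -9%) remains even when collected dates close every row open at W6 and W12, because of rows open at W24. If durations hardly vary, dropping open rows does little harm.

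The effect is confined to one descriptive secondary summary. The proportion of patients interrupted, the recorded reasons and the primary endpoint are untouched.

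**What to change.** Add to SAP 8.2.5.1:

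1. Treat an interruption that spans a visit as one record.
2. Close each 'Ongoing' row from the resumption date or next-cycle day 1 in CRF 3.8, with the nurse-call resumption date as support.
3. Leave scheduled off-treatment days out of the count. Otherwise a hold from day 25 with an on-time next cycle on day 43 becomes 43 - 25 = 18 days, although only 4 treatment days (25 to 28) were missed on the 4/2 regimen.
4. Keep permanent discontinuations separate, as the SAP already does.
5. Treat rows still open at last contact as censored. Report their number in Table 34, with a Kaplan-Meier median time to resumption or a sensitivity mean labelled as a minimum.

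The label matters. In the 14-day scenarios with variable durations, counting W24 rows only up to the visit still leaves the mean 2% to 13% low.

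Changing the CRF to carry open rows forward is not worth proposing now: Protocol 5 scheduled the end of data collection for November 2018, and SAP version 6.3 is dated 06/02/2019. The cost is one extra derivation from dates already collected, one added line in Table 34 plus the censored summary, and some durations known only as minimum values.

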3.6 Concomitant treatments

Have any symptomatic or preventive treatments been added since the last visit dated [date of last recorded visit] (including the current visit for the next cycle)? Yes No

If yes, please specify the prescriptions:

Symptomatic or preventive treatments prescribed since the last visit

- | | | |
|--|------------------------------|-----------------------------|
| Prescription of an anti-emetic treatment: |  Yes |  No |
| Prescription of an anti-diarrhoeal treatment: |  Yes |  No |
| Initiation of anti-neutropenic treatment |  Yes |  No |
| Prescription of an anti-hypertensive treatment: |  Yes |  No |
| Prescription of mouth washes and local anaesthetics: |  Yes |  No |
| Prescription of emollients, moisturising creams: |  Yes |  No |
| Prescription of analgesics: |  Yes |  No |
| Prescription of an anti-gastro-oesophageal reflux treatment: |  Yes |  No |
| Bisphosphonate treatment: |  Yes |  No |
| Other anti-tumour treatment: |  Yes |  No |

Specify: _____

Other prescriptions: Yes No

Specify: _____

e-CRF instruction:

'Please send an anonymised copy of the available prescriptions issued to the patient after the day's visit to the logistics centre, to enable the therapy management platform nurses to advise the patient. Each prescription

comprise the patient's participation no.'	
--	--

3.7 Scheduled and unscheduled medical procedures

History of calls to a healthcare professional during the previous cycle

Has the patient contacted a healthcare professional since the last documented visit dated [date of last recorded visit], excluding any cases of adverse event? Yes No

If yes, please fill in the following table for each new call to a healthcare professional:

Date	Type of call	Specialist field of the healthcare professional	Reason for the call	Action implemented
____ / ____ / _____ (DD/MM/YYYY)	 Scheduled  Unscheduled	List {General practitioner; Oncologist; Cardiologist; Nephrologist; Accident and Emergency; Nurse; Other, etc.}	 AE*; If yes, specify which one:  Other, specify: _____	 Temporary Sutent® interruption  Treatment prescribed Specify: _____  Consultation with medical specialist  Nephrologist  Cardiologist  Other: _____  Consultation with attending physician  Emergency department. Date: _____ Location: _____ Hospitalisation:  Yes  No  Hospitalisation. Date: _____ Location: _____  Hygiene and nutrition advice  Other, specify: _____  Not applicable

(Dynamic table: rows can be added if more than two consultations are observed)

*: If AE ticked, the physician has already described this AE in the previous section, the e-CRF will thus display the list of AEs already filled in and the physician can simply select the relevant AE (without having to describe it again)

History of consultations with a healthcare professional during the previous cycle

Has the patient consulted a healthcare professional since the last documented visit dated [date of last recorded visit], excluding any cases of adverse event? Yes No

If yes, please fill in the following table for each new consultation with a healthcare professional:

Date	Type of consultation	Specialist field of the healthcare professional	Reason for consultation	Action implemented
____ / ____ / _____ (DD/MM/YYYY)	 Scheduled  Unscheduled	List {General practitioner; Oncologist; Cardiologist; Nephrologist; Accident and Emergency; Nurse; Other, etc.}	 AE*. If yes, specify which one:  Other, specify: _____	 Sutent® dose modification  Temporary Sutent® interruption  Termination of Sutent®  Treatment prescribed Specify: _____  Consultation with medical specialist  Nephrologist  Cardiologist  Other: _____  Consultation with attending physician  Emergency department. Date: _____ Location: _____ Hospitalisation:  Yes  No  Hospitalisation. Date: _____ Location: _____  Hygiene and nutrition advice  Other, specify: _____  Not applicable

(Dynamic table: rows can be added if more than two consultations are observed)

**: If AE ticked, the physician has already described this AE in the previous section, the e-CRF will thus display the list of AEs already filled in and the physician can simply select the relevant AE (without having to describe it again)*

History of hospitalisations during the previous cycle

Has the patient been hospitalised since the last documented visit dated [date of last recorded visit], excluding any cases of adverse event?

Yes No

If yes, please fill in the following table for each new hospitalisation:

Date	Type of hospitalisation	Duration	Location	Reason	Action implemented
____ / ____ / ____ (DD/MM/YY YY)	 Scheduled  Unscheduled	____ days  Ongoing	 Day hospital  Hospital / University Hospital  CLCC  Private clinic  Other: _____	 AE*. If yes, specify which one:  Other, specify: _____	 Sutent® dose modification  Temporary Sutent® interruption  Termination of Sutent®  Treatment prescribed Specify: _____  Consultation with medical specialist  Nephrologist  Cardiologist  Other: _____  Consultation with attending physician  Emergency department. Date: _____ Location: _____ Hospitalisation:  Yes  No  Hospitalisation. Date: _____ Location: _____  Hygiene and nutrition advice  Other, specify: _____  Not applicable

(Dynamic table: rows can be added if more hospitalisations are observed)

**: If AE ticked, the physician has already described this AE in the previous section, the e-CRF will thus display the list of AEs already filled in and the physician can simply select the relevant AE (without having to describe it again)*

